After screening, subjects will receive the following tests: (1) Measurement of hepatic glucose production, substrate oxidation and plasma ketone/lactate/insulin/glucagon concentrations; (2) (Measurement of whole body norepinephrine turnover with ^3H -norepinephrine infusion; (3) Measurement of heart rate variability; (4) Measurement of liver fat content with ^1H -MRS; (5) 75-grams oral glucose tolerance test (OGTT)

The studies will be performed in a random order.

After the completion of the above studies, subjects in each group will be randomized (in 2:1 ratio) to receive for 12 weeks, empagliflozin 25 mg per day (n=24) or placebo (n=12), in a double blind fashion. The drug treatment will be started (day 1) on the day of the second hepatic glucose measurement (see specific details below). On day 2, the measurement of heart rate variability and norepinephrine turnover will be repeated. Subjects will continue treatment with the drug (empagliflozin or placebo) that they received during the second hepatic glucose measurement for 12 weeks and at the end of 12 weeks, all baseline tests will be repeated.

The treatment period could be extended based upon the circumstances until the repeat studies are completed.

Tests	Baseline	Day 1-3	12 Weeks
OGTT	OGTT		OGTT
HGP	Short	Long	Short
NE	NE	NE	NE
MRI	MRI		MRI
DEXA	DEXA		
HRV	HRV	HRV	HRV

The metabolic effects of empagliflozin lasted for 2 weeks in our previous studies (7). However, Ferrannini and colleagues (40) reported that at 4 weeks, the glucose effects of empagliflozin (HGP) are attenuated while the fat effects (fat oxidation and ketone production) are enhanced. Therefore, to evaluate the long term metabolic impact of SGLT2 inhibition, we decided to extend the treatment period in the current study to 12 weeks.

Specific Methods:

Screening: Medical history and physical examination will be performed. Blood samples will be drawn for CBC, blood chemistries, lipid profile, thyroid function and HbA1c. EKG will be performed.

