Data Analysis and Statistical Methods. Under steady-state postabsorptive conditions, the basal rate of endogenous glucose appearance ($R_a = bEGP$) equals $3\text{-}3\text{H}\text{-glucsoe}$ infusion rate divided by steady state plasma tritiated glucose specific activity. After drug administration, non-steady conditions for $3\text{-}3\text{H}\text{-glucose}$ specific activity prevail and the rate of whole body of glucose appearance (R_a) is calculated from the Steele equation. The difference in EGP during the last half hour of the study (390 to 420 minutes) between subjects receiving empagliflozin (Measurement II) vs placebo (Measurement I) represents the increase in EGP caused by empagliflozin. The difference in EGP between subjects receiving empagliflozin without volume repletion (Measurement II) versus with volume repletion (Measurement III) represents the role of intravascular volume depletion in the stimulation of EGP. The difference in the change in EPG between Measurement II and Measurement III will be compared to the difference between Measurement I and Measurement IV will be compared with ANOVA. Post hoc testing will be performed with Bonferroni correction for multiple comparisons.

The same statistical/analytical approach will be employed for the measurement of plasma FFA, and beta-OH-butyrate concentrations.

Sample Size Calculation. In previous studies, we demonstrated that the mean difference in EGP during the last hour of EGP measurement in empagliflozin-treated (Measurement II) and placebo-treated (Measurement I) subjects was $0.70 \pm 0.34 \text{ mg/kg}\cdot\text{min}$ (mean \pm SD) (3). To detect a 50% decrease in this difference at alpha <0.05 during the volume repletion study (Measurement III) with 90% power and alpha = 0.0125 ($=0.05/4$), we computed that 32 subjects are required. Therefore, to ensure 32 completers, we have set the sample size at 36.

Risks in Sub-Study 2:

Blood loss: blood loss in sub-study 2 will be 165 ml at each EGP measurement. Thus, the total blood loss will be 660 ml

Radiation: total amount of radiation in sub-study 2 will be 59.6 mrem (13.4 at each EGP measurement and 6 mrem at DEXA scan)

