During the Oral-IV double tracer infusion study, only the ^{14}C -glucose which escapes the liver and non-hepatic splanchnic tissues appears in the systemic circulation, while all of the infused ^3H -glucose appears in the systemic circulation. Therefore, the difference between R_a calculated with ^3H -glucose and R_a calculated with ^{14}C -glucose represents the basal rate of hepatic plus non-hepatic splanchnic tissue glucose uptake. Thus, the basal rate of EGP will be calculated for ^3H -glucose as the ^3H -glucose infusion (dpm/min) divided by the steady-state plasma ^3H -glucose specific activity (dpm/mg). The rate of ^{14}C -glucose appearance will be calculated as the ^{14}C -glucose infusion rate (dpm/min) divided by the steady-state plasma ^{14}C -glucose specific activity (dpm/mg). The hepatic and non-hepatic splanchnic glucose uptake equals $R_{a3\text{H}-\text{glucose}}$ minus $R_{a^{14}\text{C}-\text{glucose}}$. Norepinephrine clearance rate will be calculated as ^3H -NE infusion rate (dpm/min) divided by the steady state plasma ^3H -NE radioactivity (dpm/ml) (between 12 and 20 min). Norepinephrine spill over (release) rate (pg/min), which reflects the sympathetic nervous system activity (53), will be calculated as the product of plasma norepinephrine concentration (pg/ml) and norepinephrine clearance rate (ml/min). The difference between norepinephrine spill over in empagliflozin-treated and placebo-treated subjects, in each group (i.e. NGT, IFG and T2DM), represents the effect of glucosuria on the sympathetic nervous system activity. The ratio between plasma ^3H -DHPG to ^3H -NE (between 20 to 120 minutes) will be used as an index of neuronal uptake of norepinephrine (54).

Values will be presented as mean \pm SD. Difference between means will be compared by ANOVA. Post hoc testing will be performed with the Bonferroni test.

The increase in HGP caused by glucosuria in each treatment group will be related to the change in norepinephrine spill over rate with Pearson's correlation in each treatment group. We anticipate a strong correlation between the two variables.

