We anticipate that empagliflozin will increase norepinephrine spill over to the plasma in T2DM patients as well, and that the increase in norepinephrine spillover will strongly correlate with the increase in HGP. Because the methodology utilized in the present study measures the rate of total body norepinephrine spill over, it is possible that the increase in epinephrine spill over from specific organs, e.g. kidney and splanchnic (primarily hepatic) tissue, will be diluted in the systemic circulation. Thus, it is possible that only a modest effect of empagliflozin on sympathetic activity will be detected. In such a scenario, measurement of organ specific (58), e.g. renal norepinephrine spill over (with renal vein catheterization) and splanchnic (with intraduodenal ³H-NE infusion and arterial or hepatic vein sampling) can be employed to quantitate the change in sympathetic activity in the kidney and liver.

Sample Size Calculation We powered the study to detect a significant increase in the basal rate of HGP following empagliflozin administration versus placebo. In previous studies, the increase in the rate of HGP versus placebo following empagliflozin administration was 0.34 ± 0.26 mg/kg.min. Therefore, we computed that 30 subjects in 2:1 randomization (20 empagliflozin and n=10 placebo) provide >90% power to detect a significant difference in HGP between empagliflozin-treated and placebo-treated subjects (in 3 groups comparison) at alpha <0.05. Therefore, to ensure 30 completers, we have set the sample size at 36 in each group.

Item 7 Risks Section:

Complete the following table to describe the risks of all **research procedures** listed in Step 2, Institutional Form (items 28-34). *Do not list risks of Routine care procedures here.*

X N/A, Risks are described in the informed consent document – do not complete this table.

Research procedures	Risks
example: 
• History and physical• Questionnaire• Laboratory tests	List the reasonably expected risks under the following categories as appropriate:
Add or delete rows as needed	
	

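### Both sample sizes are set on completers, but the analysis text names only an ANOVA of means, with no analysis population and no way to use subjects with incomplete visits

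*Combined protocol and SAP*

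**What the plan says.** All references are to the combined protocol and SAP, Item 6.

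- **Main study, Sample Size Calculation.** The effect assumed is that "the increase in the rate of HGP versus placebo following empagliflozin administration was 0.34 ± 0.26 mg/kg.min", and "we computed that 30 subjects in 2:1 randomization (20 empagliflozin and n=10 placebo) provide >90% power". The section then says "Therefore, to ensure 30 completers, we have set the sample size at 36 in each group".
- **Sub-Study 2, Sample Size Calculation.** The same device is used: "to ensure 32 completers, we have set the sample size at 36".
- **Study Design.** After the baseline tests, subjects in each group are randomised "to receive for 12 weeks, empagliflozin 25 mg per day (n=24) or placebo (n=12), in a double blind fashion". The long HGP test is done on the day of the first dose, NE turnover and HRV are repeated on day 2, and all baseline tests are repeated at 12 weeks.
- **Data Analysis Plan.** Apart from tracer formulas and a Pearson correlation, the method is one sentence, "Difference between means will be compared by ANOVA", followed by Bonferroni post hoc tests.
- **Sub-Study 2, Data Analysis and Statistical Methods.** An ANOVA compares the II-versus-III difference in EGP with the I-versus-IV difference. Each subject has four measurements, 1 to 3 weeks apart.

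No section defines an analysis population, says whether subjects are analysed as randomised, or covers withdrawals and missing visits. The nearest provisions are in Study Design and Follow Up Visits: treatment may be extended until the repeat tests are done, and follow-up may be by telephone.

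**The concern.** The plan allows for the loss of one sixth of each randomised group but gives no rule for those subjects. A main-study subject who leaves at week 6 already has a baseline, a day-1 HGP test, and normally day-2 NE and HRV, but no week-12 result. Whether that subject counts in the acute contrasts is left open and could be settled after the data are seen.

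At week 12, an ANOVA of means uses only the subjects observed then. As named, it includes no baseline or early value, although both will have been collected. With a constant additive drug effect, it is valid if loss is unrelated to outcome within each arm, or if any selection acts equally in both arms. Otherwise the randomised comparison is disturbed.

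In Sub-study 2 the problem is different. A within-subject contrast of II minus III against I minus IV needs all four visits, so one missed visit removes the subject from it.

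**Working it through.** **Inputs.** Main study: difference 0.34 and SD 0.26 mg/kg.min, 20:10 completers, 24:12 randomised, alpha 0.05 (Sample Size Calculation and Study Design). Sub-study 2: 0.70 with SD 0.34, a 50% reduction to detect (0.35), alpha 0.0125, power 90%. Assumptions: 0.26 is a between-subject SD, and tests are two-sided (sidedness is not stated).

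**1. The plan's own figures.**
- Main study: SE = 0.26 × √(1/20 + 1/10) = 0.1007, and 0.34/0.1007 = 3.38. Power is 92.2% by the normal approximation and 90.3% by the t-test with 28 degrees of freedom. The stated figure of more than 90% reproduces for a single comparison, and 30 is the smallest total that gives it.
- Sub-study 2: a paired t-test for 0.35 with SD 0.34 × √2 = 0.481 at two-sided 0.0125 needs 31 subjects, close to the stated 32. The √2 is an assumption.
- Allowances: (36 − 30)/36 = 16.7% and (36 − 32)/36 = 11.1%. The documents state no drop-out rate.

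**2. Day-1 HGP if six per group were dropped for leaving later.**

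| Analysed | SE (mg/kg.min) | t-test power at 0.34 |
|---|---|---|
| 20:10 | 0.26 × √(1/20 + 1/10) = 0.101 | 90.3% |
| 24:12 | 0.26 × √(1/24 + 1/12) = 0.092 | 94.9% |

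The ratio of standard errors is √(0.15/0.125) = 1.095, so keeping everyone cuts the SE by about 9%. This is the full gain only if all six losses come after day 1.

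**3. Week-12 bias, under assumed selection.** If selection is the same in both arms and the drug effect is additive, the bias cancels in the difference and is 0. Suppose instead that in the empagliflozin arm alone the top sixth (4 of 24) is lost on a normal variable with correlation ρ to the HGP outcome. The cut-off is z = 0.967 and the mean of the retained five sixths is −0.250/0.833 = −0.30 SD. The shift is ρ × 0.26 × 0.30:
- ρ = 0.3: 0.023 mg/kg.min, which is 7% of 0.34 and 0.2 SE.
- ρ = 0.5: 0.039 mg/kg.min, which is 11% of 0.34 and 0.4 SE.

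Harsher inputs give more. If 4 to 6 of 24 on empagliflozin are lost and their mean response is 0.26 to 0.34 below that of completers, the shift runs from 0.26 × 4/24 = 0.043 to 0.34 × 6/24 = 0.085. The documents support no particular value.

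**4. Do the tests match across visits?** NE turnover and HRV are the same test at baseline, day 2 and week 12. HGP is not: the day-1 test is the long one, with non-steady-state calculation after dosing, while baseline and week 12 use the short basal test. One repeated-measures model fits NE and HRV directly but needs justification for HGP.

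**The case against.** Sizing on expected completers is routine and does not say who is analysed. The word occurs only in the two sample-size sentences. The Data Analysis Plan defines the effects as differences between empagliflozin-treated and placebo-treated subjects, with no restriction to those who finish. A reader might infer that the plan discards randomised data or counts only completers; the text does not say so. The day-1 gain therefore arises only if analysts would drop dosed subjects who have a valid test. The power target is met with 30 in any case.

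A reader might also infer that adverse effects will cause drop-out on empagliflozin alone, citing the risk list. That list belongs to Sub-study 2, where subjects take two tablets, and it gives no drop-out rate. It cannot carry a claim about the 12-week study.

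Nor does the drop-out argument extend to Sub-study 2. No randomisation is stated there, it has no 12-week endpoint, and a subject missing one visit can still enter some of the pairwise comparisons.

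Extending treatment should reduce missing week-12 tests, and telephone contact helps to keep subjects in follow-up. Neither is an analysis rule.

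These objections stand. They limit the point but leave the gap: no analysis set, no handling of missing visits, and a method that leaves collected data unused.

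**Conclusion.** The point holds in a limited form. The plan sizes on completers and is silent on who is analysed and how partial data are used. For the acute HGP contrast the avoidable cost is at most a rise in SE from 0.092 to 0.101 mg/kg.min and a fall in single-comparison power from 95% to 90%, if six per group would otherwise be dropped.

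The size of any week-12 bias is unknown. It starts at 0 and reaches about 0.04 mg/kg.min with one-arm selection at an assumed correlation of up to 0.5; larger values need stronger assumptions. Drop-out bias and disturbed randomisation are claims about the main study only. In Sub-study 2 the loss is of incomplete sets of four visits, and its size is not estimated here.

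This does not invalidate the trial. It should be settled before analysis, because the stated ANOVA has a better alternative that uses data already being collected.

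**What to change.** In the Data Analysis Plan:

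1. Analyse the acute HGP, NE and HRV contrasts in every randomised, dosed subject who has that test, whether or not the subject reaches week 12.
2. Analyse NE and HRV by randomised arm in a mixed model with baseline value, arm, visit, arm-by-visit and unstructured covariance. For HGP, either justify the same model or, because the day-1 and week-12 tests differ, fit separate baseline-adjusted models for each visit and use the early value to handle missing week-12 results.
3. Report losses and reasons by arm, and give the completer analysis as a sensitivity analysis.

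In the Sub-Study 2 analysis section, replace the ANOVA with a mixed model with drug, fluid, drug-by-fluid and a subject effect, so that subjects with two or three visits contribute.

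The cost is analysis text and slightly more programming; no visits or subjects are added. The models assume that data are missing at random given what was observed. They do not remove bias if drop-out depends on the unobserved outcome in a way the recorded values do not capture, so the losses by arm must still be read alongside the result.
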